3. Log call in coversheet, including answers to any follow-up questions you had when confirming eligibility, and any concerns they brought up and how they were/will be addressed
4. Check SurveyMonkey for consents every day
5. Every 2 days, follow up with those who expressed interest but haven't completed consent, alternating phone calls and emails
 - a. Log contacts with them in coversheet

Step 4: Logging Consent & Randomization Info

1. Check daily to see if the completed their consent/baseline
2. Create a Word Doc of their consent and HIPAA to send with their baseline email
 - a. Open up the Consent & Consent Addendum templates
 - b. Go to the therapist consent form on SurveyMonkey
 - c. Make sure you are on the “Individual Responses” tab.
 - d. Copy and paste the information underneath the word “Complete” in the grey text box into the bottom of the consent template.
 - e. Copy and paste all of the pages of questions and responses between (but not including) the Contact Info Page and the HIPAA into the consent form template
 - f. Rename the template by replacing the word “Template” in the title with (Therapist last name and first initial)
(example: !Template.Pilot-TherapistConsentForm → [name]-Pilot.TherapistConsentForm)
 - g. Save document as PDF
 - h. Open up the Signed HIPAA template
Make sure you are on the “Individual Responses” tab.
 - i. Copy and Paste the information underneath the word “Complete” in the grey text box into the bottom of the HIPAA template.
 - j. Copy and paste the HIPAA page questions and answers at the bottom of the HIPAA template
 - k. Rename the template by replacing the word “Template” in the title with (Therapist initials)
(example: !Template.Pilot-TherapistHIPAA → [name]-Pilot.TherapistHIPAA)
 - l. Save document as PDF
3. Log the date they completed the consent in the [Summative Tracking DB](#)
4. Assign the therapist a study ID and record it in the SSID column in the [Summative Tracking DB](#)
5. Record the randomization categories for the participant in the ‘Randomization’ tab in the [Summative Tracking DB](#).

Step 5: Randomization

1. Check that the randomization information is entered into the ‘Randomization’ tab in the [Summative Tracking DB](#)
2. Email [name] (or person responsible for randomizing) to request they randomize the participant
3. To Randomize:
 - a. Open Minim Py
 - b. Enter in the randomization categories

WILLOW Full RCT Therapist Protocol

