PracticeGround: Transforming Training and Delivery of Mental Health EBPs

NCT02314624 | Statistical Analysis Plan | February 8, 2020

Analysis Strategy

We conducted all analysis in IBM SPSS V19. We used the Generalized Linear Model to examine the between-condition change over time on study outcomes. The effects of primary interest were those reflecting the effects of WILLOW. For outcomes measured at baseline and follow-up points, that was the Time X Condition effects (measuring between-condition change from baseline). For outcomes measured only at follow-up points (e.g., therapeutic alliance and use of evidence-based therapy tasks), that was the Condition effects since they would represent average between-condition differences during the time patients received services. As previously mentioned, providers completed questionnaires for each study patient they treated. Hence, the provider sample size reflects the number of patients they answered about, not the number of providers. Several providers participated in the study concurrently with multiple patients. Patients were included in the analyses only if they attended five or more sessions with a participant provider.

Preliminary analyses provided important information guiding our strategy. First, we found no statistically significant differences between conditions on baseline measures. Second, we computed the design effects due to this nested design to determine the extent to which the intraclass correlation due to clustering and size of the cluster affected the analyses. Design effects ranged up to 1.8. Because all were under 2.0, we did not adjust analyses to account for clustering effects (Muthén & Satorra, 1995). For providers meeting participating in both studies, we used their Study 1 data for outcomes except for outcomes measured only in Study 2. For those outcomes, we used their Study 2 data.

References

Muthén, B.O. & Satorra, A. (1995). Complex sample data in structural equation modeling. *Sociological Methodology*, 25, 267-316. doi: 10.2307/271070

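### Therapists are assigned to condition, yet the SAP ignores clustering because design effects are under 2.0; at the stated maximum of 1.8 a nominal 5% test can run at about 14%

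*SAP*

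**What the plan says.** The Therapist Protocol randomises therapists (Step 2, consent call script; Step 5). Staff use a program called Minim Py, in which they "Enter in the randomization categories". Step 4 has the categories logged for each therapist in the tracking database. Neither document names them. A patient takes the condition of his or her therapist (Patient Protocol, Step 3).

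The SAP (Analysis Strategy) uses a Generalized Linear Model and lists no covariate. For outcomes with a baseline, the effect of interest is described thus: "that was the Time X Condition effects (measuring between-condition change from baseline". For the others: "For outcomes measured only at follow-up points (e.g., therapeutic alliance and use of evidence-based therapy tasks), that was the Condition effects". On clustering it reports "Design effects ranged up to 1.8" and concludes: "Because all were under 2.0, we did not adjust analyses to account for clustering effects". Provider questionnaires are counted once per patient, not once per provider.

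**The concern.** When whole therapists are assigned to a condition, patients of the same therapist do not give independent information about the condition effect. A design effect of 1.8 means that the true variance of the contrast is 1.8 times the one the model reports. Standard errors are then too small and false positives too frequent. The SAP reports this figure and then sets it aside by a threshold.

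A second matter bears on the repair. If allocation was balanced on categories that predict outcome, part of the between-therapist variance is removed from the condition contrast. A model that omits the categories still counts that part in its standard error. Correcting clustering alone could then overshoot, and adding the categories alone would shrink a standard error that is already too small. At stake are the false-positive rate now, and avoidable loss of power afterwards.

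**Working it through.** **Inputs from the documents.** Therapist as the unit assigned (Therapist Protocol, Steps 2 and 5). 2 to 5 patients requested per therapist (Step 2); realised numbers are not given. Maximum design effect (DE) 1.8 (SAP); the outcome it belongs to is not given.

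**Assumptions.** Two-sided 5% level (the SAP states none). Linear outcome, one value per patient. Categories balanced between arms and explaining a share f of between-therapist variance, 25% or 50%. DE 1.5 and 1.2 as milder cases.

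**Step 1: the plan's own figure.** DE = 1 + (m − 1) × ICC, with m patients per therapist. Without m and ICC, 1.8 cannot be reproduced, only inverted: ICC = 0.8 / (m − 1) = 0.80, 0.40, 0.27, 0.20 for m = 2, 3, 4, 5.

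**Step 2: clustering ignored, categories not prognostic.** True level = 2 × [1 − Φ(1.96 / √DE)].
- DE 1.8: 1.96 / √1.8 = 1.46, level 14.4%
- DE 1.5: 1.96 / √1.5 = 1.60, level 11.0%
- DE 1.2: 1.96 / √1.2 = 1.79, level 7.4%

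**Step 3: categories balanced and prognostic, follow-up-only outcomes.** On a scale where the SAP's reported variance is 1, the true variance is V = DE − m × ICC × f, and the true level is 2 × [1 − Φ(1.96 × √(reported / V))]. With DE 1.8, m = 5 and ICC 0.20:
- f = 25%: V = 1.8 − 5 × 0.20 × 0.25 = 1.55
- f = 50%: V = 1.8 − 5 × 0.20 × 0.50 = 1.30

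| Analysis | Reported variance | Level at f = 25% / 50% |
|---|---|---|
| SAP as written | 1 | 11.5% / 8.6% |
| Categories added, clustering ignored | 1 − ICC × f = 0.95 / 0.90 | 12.5% / 10.3% |
| Clustering corrected, categories omitted | DE = 1.8 | 3.5% / 2.1% |

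In the last row the standard error is √(1.8 / 1.55) = 1.08 to √(1.8 / 1.30) = 1.18 times what it should be. At DE 1.2 and m = 5 (ICC 0.05) the three rows are 6.6 / 5.9%, 6.8 / 6.2% and 4.4 / 3.8%.

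With m = 2, m × ICC = 2 × (DE − 1). At f = 50%, V = DE − (DE − 1) = 1, so the SAP's test is exactly at 5.0% whatever the DE. At f = 25% and DE 1.8, V = 1.40 and the level is 9.8%.

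**Step 4: simulation check.** Assumed: 24 therapists with 5 patients each, two binary categories, minimisation probability 0.9, DE 1.8, 6000 runs (Monte Carlo error about 0.3 points at 5%). Levels at f = 0 / 25 / 50%:
- SAP: 15.0 / 11.5 / 9.7%
- Categories only: 15.4 / 12.3 / 11.1%
- Clustering only (therapist means): 5.3 / 3.5 / 2.4%
- Both: 5.4 / 4.8 / 5.1%

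In a separate run (30 therapists, 3 patients each, 60% explained), clustering correction alone gave 1.7% under minimisation and 4.9% under plain randomisation. The conservatism therefore comes from the balancing.

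**Step 5: Time X Condition outcomes.** A category that shifts only the outcome level cancels in the change from baseline. In simulation (DE 1.8 assumed to apply to change), the SAP's test ran at 15.3 / 14.0 / 14.6% and the clustering-corrected test at 5.0 / 4.8 / 4.9%, already nominal without categories. The form of the correction matters. In three simulated data sets with therapist variance in change, therapist and patient random intercepts gave standard errors of 0.1744, 0.1649 and 0.1702, identical to the unadjusted change analysis. Therapist means gave 0.2626, 0.2243 and 0.2643.

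**The case against.** The strongest reply is that the documents establish only the clustering error. The categories are unnamed, their prognostic strength is unknown, and minimisation is inferred from the program's name. Balance may also be imperfect: re-enrolled pilot therapists keep their condition (Therapist Protocol, Step 6), and the analysis set is restricted after allocation ("Patients were included in the analyses only if they attended five or more sessions with a participant provider"). All of this stands. It makes the category part conditional and secondary, and leaves the clustering part untouched.

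A second reply is that 1.8 is a maximum, so many outcomes may be only mildly affected. That is fair, and the 7.4% at DE 1.2 shows it. But the SAP does not say which outcomes are which.

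Three stronger readings are tempting and not supported:
- **That every test in the SAP is too liberal.** With 2 patients per therapist and categories explaining half the between-therapist variance, the level is 5.0%.
- **That omitting the categories makes the present follow-up-only tests conservative.** At DE 1.8 and 5 patients per therapist they are inflated at both assumed values of f. Conservatism would appear only after clustering is corrected.
- **That baseline testing was the reason for having no covariates.** The SAP lists it among its preliminary analyses ("First, we found no statistically significant differences between conditions on baseline measures") but does not draw that link.

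**Conclusion.** The concern holds. The threshold of 2.0 does not justify ignoring clustering: at the SAP's own maximum, a nominal 5% test runs at about 14.4% if the categories are not prognostic. If they are balanced and prognostic, the inflation shrinks and can disappear in small clusters. A clustering correction without them would then cost power on follow-up-only outcomes. For Time X Condition outcomes this applies only if the categories also predict change.

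The clustering conclusion rests on the SAP's design effect and an assumed two-sided 5% level. The category figures rest on assumed cluster size, f and balance, and f cannot be computed from the documents. All figures use one value per patient. The repeated week 4, 8 and 12 measures, for which the SAP states no correlation structure, are not modelled.

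**What to change.** 1. Re-run all outcomes with a therapist-level cluster-aware analysis: random effects, or cluster-robust standard errors with a small-sample correction. For Time X Condition outcomes the random part must include therapist by time.
2. Replace the threshold rationale, and report the design effect for each outcome.
3. Present this as a disclosed re-analysis, since the SAP is written in the past tense.
4. Within that model, name the randomisation categories and their levels. Include them for follow-up-only outcomes, and as category by time for outcomes with a baseline. Never add them without the clustering correction.
5. First check that the categories exist for re-enrolled pilot therapists and for the providers covered by this rule: "For providers meeting participating in both studies, we used their Study 1 data for outcomes except for outcomes measured only in Study 2". Say how providers without them are handled. Check also that the levels are few relative to the number of therapists.

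**Cost.** SAP wording, a re-run, wider intervals and some therapist-level degrees of freedom. The following power figures assume a 0.6 SD effect, DE 1.8 and 24 therapists with 5 patients each. Adding two binary categories to the clustering-corrected analysis moves simulated power from 64.4% to 63.4% if they are not prognostic, from 65.6% to 70.1% at f = 25%, and from 66.5% to 77.9% at f = 50%. A single 8-level category that is not prognostic lowers it from 64% to 59%, which is why the number of levels must be known first.

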- You will be randomized to one of two conditions: the WILLOW condition or standard care condition.
- If you are randomized to the WILLOW condition, you will be asked to use a computer in session to guide you through conducting Behavioral Activation for the treatment of depression.
- If you are randomized to the standard care condition, you will be asked to conduct treatment as you normally would.
- In both cases, we will ask that you meet with 2-5 research patients for 12 weeks each. You can choose to treat as many study patients as your schedule allows. Patients that

WILLOW Full RCT Therapist Protocol

are enrolled in the study with you will need to be new patients to your clinic and must not have received treatment from you previously.

- You can still use WILLOW with your patients who are not involved in the research study.
- Participants in both conditions will be asked to complete one online survey before starting the study (baseline) and another set of online surveys with a brief telephone interview after 4, 8 and 12 weeks for each research patient they treat. You will be compensated \$50 for each 4 week and 8 week survey, and \$60 for each 12 week survey you complete.
- You will be eligible to obtain free access to WILLOW for 12 months after the completion of your participation, which involves successfully recruiting at least 1 study patient and completing all assessments for that patient.

Does this sound like something you would be interested in?

If no, thank them for their time and hang up.

If yes, proceed to the next section.

Awesome! The next step would be for you to read and sign a consent form.

The entire process takes about 15-20 minutes. I will send you an email shortly that contains the link to the consent form and we ask that you complete it within the next two days. After completing the consent form, we will randomize you to either the WILLOW condition or the standard care condition and follow up with orientation brief call to explain the next steps.

Do you have any last questions for me?

Thank you so much for your interest in our research. Please don't hesitate to contact us if you have any questions as you are reviewing the consent form. Have a great day!

Step 3: Send Consent Survey

1. Send therapist consent survey email
2. Log date consent sent in the [Summative Tracking DB](#)

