We will ask that you complete three additional study assessments for each study patient you treat. These will take place at weeks 4, 8, and 12 of your patient's study treatment. We've worked to keep the study assessments as convenient as possible. Surveys at Weeks 4 and 8 will consist of a brief phone interview lasting approximately 10-15 minutes and then an online survey that may take about 15-20 minutes. You will be compensated \$50 for each week 4 and 8 survey you complete. The Week 12 assessment will consist of a phone interview that will last about 30 minutes and the online survey that will take another 30 minutes. You will be compensated \$60 for each week 12 survey you complete. During your final study assessment, you will be asked to provide information about the exact number of sessions you conducted with each of your study patients. In order to help you track these assessments, we will provide you with a session tracking sheet for your convenience.

<<for pilot therapists make sure to point out that we will not be doing amazon giftcards anymore, both for therapists and patients>>

If WILLOW Condition:

WILLOW Full RCT Therapist Protocol

<<if therapist did pilot, then they do not need to do the feature review. Skip to last paragraph>>
After our next call, we will provide you access to WILLOW and the training resources. We will also work with you to come up with a tailored training plan to meet your learning style and needs so that you can feel prepared to use WILLOW in-session. Once you have explored WILLOW and understand how to use it, we will schedule a WILLOW Feature Review with one of our study staff and ask that you demonstrate some of the WILLOW features to us. (Don't worry, you can retake the feature review up to 2 times and we will provide you with a study guide!). You'll receive \$100 for passing this review. After you complete the feature review, you will be ready for your first study patient to use WILLOW with.

Again, we will review the study procedures in depth during our next call, but do you have any questions about this right now?

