Wonderful! Thanks so much for taking the time to talk with me today. I will send you an email right after we hang up that includes a copy of your signed consent form for your records and the link to the baseline assessment. Remember, we will need you to complete the surveys within the next 48 hours. If you have any questions as you are completing the surveys, please contact us immediately. We're here to help! I look forward to talking with you again on **[day, date, time that you scheduled orientation call]**!

2. Send therapist the Baseline Survey email and attach their signed consent form and HIPAA authorization
 - a. Make sure to attach their signed HIPAA and Consent form.
 - b. Check every day
 - c. Send reminder email if Baseline surveys are not completed within 48 hours, baseline must be done before orientation call
3. Record all scheduling information in Summative Tracking DB, including when orientation call is scheduled, when BL surveys were sent

Step 7: Therapist Orientation Call

1. If they don't pick up, leave a voicemail and send appropriate email, script below.
2. Call them back every 2 days until you reach them.

Voicemail Script:

Hi this is _____ from the Depression Treatment Study. Sorry we missed you. I had in my calendar that we were scheduled to speak today, Day, Date at Time. If you receive this message in the next few minutes, please give me a call back at (phone #). Otherwise, we would love to reschedule a time to review the study procedures and the next steps for your participation. We are eager to get started and I hope to talk with you soon. Please give us a call back at (phone #)

WILLOW Full RCT Therapist Protocol

when you have 15-20 minutes to talk or let us know when a good time for us to call you back would be.

3. If they call you back

- a. And it is a good time for you to talk: Go through the script below
- b. And it is not a good time for you to talk: Schedule a time you can call them back.
 - i. Log call time and date in the Pilot RCT Calendar
- c. Log the call in the cover sheet

4. If they pick up, use the script below:

Calling Script:

Hi, this is _____ and I'm calling from the Depression Treatment Study. Thank you for completing our baseline survey! We would like to tell you more about our study procedures at this time. Is this a good time to talk?

If it is, proceed.

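### Provider outcomes are counted per patient but have only one baseline per provider, so the Time X Condition test on any provider outcome with a baseline appears to reuse that value and generally has the wrong error rate

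*SAP*

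**What the plan says.** **Survey schedule.** In the Therapist Protocol, Step 2 (Informed Consent Phone Call), therapists in both arms are told that they will "complete one online survey before starting the study (baseline) and another set of online surveys", the latter at weeks 4, 8 and 12 and separately for each study patient. Step 6 (Therapist Warm Phone Call & Baseline Survey) repeats this: "We will ask that you complete three additional study assessments for each study patient you treat". The same step adds that "baseline must be done before orientation call". The baseline therefore precedes every study patient and cannot concern any one of them.

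**Patients per provider.** Step 2 plans for 2-5: "we will ask that you meet with 2-5 research patients for 12 weeks each". It also ties later free access to the software to recruiting one patient, so providers with a single patient are foreseen. The SAP says only that "Several providers participated in the study concurrently with multiple patients", and it drops patients who attended fewer than five sessions.

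**Analysis.** In the SAP, Analysis Strategy, "the provider sample size reflects the number of patients they answered about, not the number of providers". The reason given is that providers filled in questionnaires about each patient. Outcomes with a baseline are tested by Time X Condition in a Generalized Linear Model. On clustering the SAP reports that "Design effects ranged up to 1.8" and, since every value was below 2.0, applies no adjustment.

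**The concern.** The reason for counting provider data by patient is true of the follow-up surveys and false of the baseline. If the provider sample size is the number of patients and change is measured from baseline, every patient record needs a baseline value, and a provider with three patients has only one to give. The natural way to fill the records is to repeat it.

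Repeated values carry no new information. All of a provider's change scores then share the same baseline error, and a test that treats them as separate understates the uncertainty of the arm difference. At stake are the p-values and the apparent sample size for provider outcomes measured both before and during treatment. Provider wellbeing, which Therapist Protocol Step 7 says will be assessed, is a candidate, but no document lists which provider measures were taken at both times.

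**Working it through.** **Inputs.** From the documents: one baseline per provider, three follow-ups per patient, 2-5 patients planned per provider (m), largest design effect 1.8, no clustering adjustment. Not in the documents and therefore assumed: two-sided 5% level; 40 providers in total, split equally (20 in some runs); total variance 1, made up of provider 0.1-0.7, provider-by-occasion 0 or 0.2, patient 0-0.3 and residual 0.2-0.6.

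**1. The SAP's own figure.** DEFF = 1 + (m - 1) x ICC. Setting DEFF = 1.8 gives ICC = 0.8/(m - 1), which is 0.8, 0.4, 0.27 and 0.2 at m = 2, 3, 4 and 5. The SAP gives neither ICC nor m, so 1.8 cannot be reproduced. Ignoring a design effect of 1.8 in a simple comparison of arms gives an actual level of 2 x [1 - Phi(1.96/sqrt(1.8))] = 2 x [1 - Phi(1.461)] = 0.144.

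**2. What a repeated baseline does to that figure.** Identical values have ICC 1, so DEFF = 1 + (m - 1) = m. That is 2 to 5 at the planned 2-5 patients, but 1.8 at an average of 1.8 analysed patients.

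**3. Change from a repeated baseline.** With equal residual variance v at both times, a patient-level change score has variance 2v. Two patients of the same provider share the baseline error, so their covariance is v and the ICC is v/2v = 0.5. Then DEFF = 1 + (m - 1)/2 = (m + 1)/2.

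| m | DEFF | 1.96/sqrt(DEFF) | Actual level |
|---|---|---|---|
| 1.7 | 1.35 | 1.69 | 0.09 |
| 2 | 1.5 | 1.60 | 0.11 |
| 3 | 2 | 1.39 | 0.17 |
| 5 | 3 | 1.13 | 0.26 |

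**4. Simulation under no effect.** Repeated baseline, 40 providers, equal m, one or three follow-ups, 2,000 trials per setting (Monte Carlo standard error about 0.5 percentage points). Ranges run over the variance splits.

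| m | Allowing only for correlation within a patient record | All rows independent | Provider-level change |
|---|---|---|---|
| 2 | 11-14% | 0.4-9% | 4-5% |
| 3 | 17-21% | 2-16% | 5-6% |
| 5 | 25-30% | 5-25% | 4-5% |

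Further runs put the top of the patient-level range at m = 5 at about 33%. With unequal numbers of patients averaging 1.6 to 1.8, patient-level change tests rejected in about 9-15% of trials in most settings, 17% at the highest. With one patient per provider nothing is repeated, and tests that allow for correlation within a person are near nominal (about 6%).

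**5. If the baseline was entered once instead.** An independent-row model then rejects in about 0-4% of null trials. It is conservative, because it ignores the correlation between a provider's baseline and follow-up.

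**6. Candidate remedies under the same assumptions.** Provider-level analysis adjusted for baseline: 4-6%. Standard errors clustered on provider, even on repeated rows: 4-8%. A provider random intercept added to repeated rows: 10-39%, because it treats the copies as independent readings and shrinks the residual variance.

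**The case against.** The strongest reply is that the SAP never says the baseline was repeated. A linear model on long data accepts one baseline row per provider and several follow-up rows, and the SAP refers back to text outside these documents that may describe the layout. This stands: repetition is an inference from the sample-size sentence. It does not remove the problem, since entering the value once in an independent-row model also misses the nominal level, in the other direction.

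Second, no affected outcome is named. The SAP's two examples, alliance and use of therapy tasks, are measured only at follow-up, and each patient has their own baseline. This also stands and limits the reach of the point.

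Third, a reader might infer that a repeated baseline contradicts the SAP's statement on design effects, because 2-5 patients per provider would give values of 2-5. The documents do not support that. The planned number is not the analysed number, single-patient providers are foreseen, patients with few sessions are excluded, and an average of 1.8 or fewer patients is compatible with both repetition and a maximum of 1.8.

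Fourth, the highest error rates, up to 39%, belong to a random-intercept model that the SAP does not use. They are a warning about one repair, not a measure of the analysis as written.

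**Conclusion.** The point holds in a limited form. The mismatch between one baseline per provider and a per-patient sample size is explicit, and the SAP's reason for that sample size fails at baseline. For provider outcomes with a baseline, and where providers have two or more analysed patients, a repeated baseline generally gives the Time X Condition test the wrong error rate. For patient-level change tests this is about 9-15% at an average of 1.7-2 patients and up to about 33% at 5.

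A reader might infer that the p-values are always too small. They need not be: an independent-row model runs from about 0 to 24%, and the SAP does not state its subject variable, covariance structure or variance estimator. All sizes rest on assumed variances, an assumed 40 providers and an assumed two-sided 5% level. The repetition itself is the natural reading of the SAP, not something it states.

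**What to change.** State how the single provider baseline was entered and which provider outcomes have both a baseline and a follow-up. For those outcomes, take the baseline out of the repeated rows and use it once per provider as a covariate. Test Condition on the follow-up data, either on provider means or with random effects for provider and for patient within provider, using small-sample degrees of freedom. With equal numbers of patients per provider the two give the same test. Standard errors clustered on provider are an acceptable alternative. Do not simply add a provider random intercept to repeated baseline rows.

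Report the number of providers per arm beside the number of patient records, together with the cluster sizes and ICCs behind the design effects.

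The cost is a change to the SAP wording and a re-run on data already held, with a smaller effective sample size for these outcomes.
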